3.14.1.4 Key Secondary Efficacy Endpoints Analysis

The key secondary efficacy endpoint analyses for the DEP are provided below. These analyses will be performed on the DEP FAS.

- ***Change from baseline in blood Phe level at last measurement of the iTD of SYNB1934v1***

The key secondary endpoint, change from baseline in blood Phe level at last measurement of the iTD of SYNB1934v1, will be analyzed using an MMRM analysis similar to the analysis methodology model described for the DEP primary efficacy analysis ([Section 8.4](#)), with the dependent variable being the change in blood Phe level from DEP baseline.

- ***A ≥ 20% reduction from baseline in blood Phe level at any time in the DEP***

The number and proportion of participants meeting this criterion will be summarized along with [REDACTED]. As discussed in [Section 3.14.1.1](#), this analysis will not consider the additional blood Phe data from DEP Weekly substudy. Note this will consider all Week 3 post-baseline blood Phe values occurring in the DEP. This will be an observed-case analysis approach using the DEP FAS such that if a participant is missing the data needed to determine the endpoint, they will be considered as not having met the endpoint.

3.14.1.5 Key Secondary Sensitivity and Supplementary Analysis

- ***Change from baseline in blood Phe level at last measurement of the iTD of SYNB1934v1***

- ***Analysis by iTD:*** The analysis will be performed on each iTD subgroup.
- ***Imputation of Missing Data:*** Multiple imputation will be used to impute missing blood Phe data during the DEP. The imputation of missing data will assume the data is missing at random (MAR). The methodology for the multiple imputation and analysis is provided in [Section 3.18.1](#). The analysis model will be the same model as the DEP key secondary endpoint analysis. This analysis will be performed on the DEP FAS population.
- ***Analysis of Covariance:*** The change from baseline in blood Phe level at last measurement of the iTD of SYNB1934v1 endpoint will be analyzed using an ANCOVA model. The change from DEP baseline in blood Phe level at the last measurement of the iTD of SYNB1934v1 will be the dependent variable, using the average of the duplicate blood Phe levels (i.e., if one of the values is missing, the non-missing value will be used). The ANCOVA has Treatment as a fixed effect and DEP baseline Phe is a covariate. This will be an observed-case analysis using the DEP FAS population, missing data will not be imputed.

- ***Excluding Observations after Treatment Discontinuation, Antibiotic use, or Prohibited Medication:***

Medication: The key secondary efficacy endpoint analysis will be performed on the DEP FAS using an observed case analysis which excludes observations after the following intercurrent events occur in the DEP: Treatment discontinuation, antibiotic use, prohibited medication use.

- ***RWP PPS Analysis:*** The analysis will be performed using the responder RWP PPS analysis set (defined in [Section 3.5](#)).

- ***MMRM Analysis by Dose Level:*** The change in blood Phe level will be analyzed using an MMRM model. All available Week 3 blood Phe data will be used. The model will have change from baseline as the dependent variable. Dose level (as a categorical variable) and baseline blood Phe will be fixed effects. The MMRM analysis will be based on the restricted maximum likelihood method. A Kenward-Roger approximation will be used for the denominator degrees of freedom. The covariance structure for the repeated-measures will be a direct product of unstructured for the multiple Week 3 visits (i.e., a total of 5 possible Week 3 visits, 3 for each dose level and 2 for possible repeats of the 3×10^{11} and 6×10^{11} doses) and compound symmetry for the repeated assessments at a particular visit. As such the covariance structure will use the direct product structure “UN@CS” as defined in SAS PROC Mixed.

This will be an observed-case analysis, this analysis will be performed using the DEP FAS and also using the responder RWP FAS population, missing data will not be imputed.

If the MMRM analysis does not converge, the repeated measures at each blood Phe assessment will be averaged together and the average of the repeated measures will be used to calculate the percent change in blood Phe level, the dependent variable. The model will have change from baseline as the dependent variable (i.e., using the averaged value at Week 3 visit). The MMRM model will be the same (i.e., same set of fixed effects) with the exception that the covariance structure for the repeated-measures will be unstructured for the multiple Week 3 visits (i.e., a total of 5 possible Week 3 visits, 3 for each dose level). If this model does not converge a compound symmetry covariance structure will be used.

- ***A ≥ 20% reduction from baseline in blood Phe level at any time in the DEP***

- ***Analysis by iTD:*** The analysis will be performed on each iTD subgroup.

- ***Imputation of Missing Data:*** Multiple imputation will be used to impute missing blood Phe data during the DEP. The imputation of missing data analysis will assume the data is missing at random (MAR). The methodology for the multiple imputation is provided in [Section 3.18.1](#). The number and proportion of participants meeting this criterion will be summarized along with [REDACTED] based on the imputed data. This analysis will be performed on the DEP FAS population.

- ***Excluding Observations after Treatment Discontinuation, Antibiotic use, or Prohibited Medication:***

Medication: The key secondary efficacy endpoint analysis will be performed on the DEP FAS using an observed case analysis which excludes observations after the following intercurrent events occur in the DEP: Treatment discontinuation, antibiotic use, prohibited medication use.

- **RWP PPS Analysis:** The analysis will be performed using the responder RWP PPS analysis set (defined in [Section 3.5](#)).

3.14.1.6 Control of Multiplicity

The overall Type I error rate for the DEP will be controlled at the 2-sided [REDACTED] for the primary endpoint. If the DEP primary endpoint analysis is significant at the 2-sided [REDACTED] the key secondary endpoint, change from baseline in blood Phe level at last measurement of the iTD of SYNB1934v1, will be tested at the 2-sided [REDACTED] level.

Note that the dichotomous DEP key secondary endpoint, a $\geq 20\%$ reduction from baseline in blood Phe level at any time in the DEP, does not have an associated inferential test.

3.14.1.7 Secondary Efficacy Endpoints Analysis

The following are the analysis methods for the DEP secondary efficacy endpoints.

- **Blood Phe level $\leq 360 \mu\text{mol/L}$ at any time of the iTD of SYNB1934v1**
- **Blood Phe level $\leq 360 \mu\text{mol/L}$ at any time in the DEP**

For each of these 2 endpoints, the proportion of participants meeting the endpoint will be summarized along with [REDACTED] confidence intervals. This will be an observed-case analysis approach using the DEP FAS such that if a participant is missing the data needed to determine the endpoint, they will be considered as not having met the endpoint.

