#### **4.2.1. Participant Inclusion Criteria**

1. Age  $\geq 18$  years.
2. Able and willing to voluntarily complete the informed consent process
3. Diagnosis of PKU and failure to maintain recommended blood Phe levels on existing management (sapropterin, sepiapterin and/or Phe-restricted diet), demonstrated by uncontrolled blood Phe level  $> 360 \mu\text{mol/L}$  on current therapy any time during screening and uncontrolled blood Phe level  $> 360 \mu\text{mol/L}$  on current therapy when taking the average of the 3 most recent Phe levels from the participant's medical history (inclusive of any screening values). All screening values must be obtained more than 7 days apart, as determined by central or local laboratory.

4. Females of childbearing potential must have a negative pregnancy test at screening and the end of DEP (in order to enter Part 2) and RWP (in order to enter Part 3) and be willing to have additional pregnancy tests during the study.
5. Sexually active female participants of childbearing potential must be willing to use an acceptable method of contraception while participating in the study and for 2 weeks after the last dose.
6. Stable diet including stable medical formula regimen (if used) for at least 1 month prior to screening.
7. If using sapropterin or sepiapterin, must be on a stable dose for at least 3 months.
8. Willing and able to continue current diet, sapropterin, sepiapterin and large neutral amino acids unchanged during screening, DEP, and RWP and to engage in all study activities.

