### 5.3. Randomization

At the end of the DEP, after completing 3 weeks of dosing at their iTD, participants will be randomized 1:1 to receive either SYN1934v1 at their iTD established in the DEP or placebo, stratified by the qualifying blood Phe value from screening. This screening value will be the value determined by the central lab, except for participants where the local screening value was  $> 360 \mu\text{mol/L}$  and the central screening value was  $\leq 360 \mu\text{mol/L}$ , in which case the local screening value will be used for stratification. Stratification will be based upon screening blood Phe levels of 361 to 720  $\mu\text{mol/L}$  or  $> 720 \mu\text{mol/L}$ . This stratification has been selected to dichotomize the participant population by control, based upon prior surveys of patients with PKU.

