3.3 Blood Phe Values at Baseline and Post-Baseline Visits

Baseline for blood Phe level in each of the 3 parts of the study will be defined as the mean of the duplicate blood Phe level measurements at the first visit of that part. If only one blood Phe level measurement is available, then that measure will be used as baseline. If the measurement at the first visit is missing, the most recent non-missing blood Phe levels from the central lab to the visit will be used (i.e., blood Phe levels from the local labs will not be used for analyses but can be used as for the inclusion criterion).

As defined in the schedule of events ([Table 11](#) and [Table 12](#)), the Part 2 RWP baseline is the End of the DEP visit, and the OLE baseline is the Part 2 RWP Week 4 visit.

Similarly, for the determination of responders and participants who achieve a specific reduction in Phe (e.g., Phe level $\leq 360 \mu\text{mol/L}$ at any time in the DEP, or a $\geq 20\%$ reduction from baseline), and in situations where a single-Phe value is needed for a particular visit (e.g., summary statistics over time), the mean of the duplicate blood Phe level measurements at the applicable post-baseline timepoint (e.g., Week 3) will be used. If only one of the duplicate blood Phe levels is available at a particular post-baseline timepoint, then that measurement will be used. Unless otherwise specified in the SAP, only the MMRM analyses of blood Phe will use the duplicate blood Phe assessments, all other summaries will use the average of the duplicate blood Phe measurements.

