3.14.1.8 Exploratory Endpoints Analysis

The following are the analysis methods for the set of DEP exploratory endpoints. These analyses will be performed on the DEP FAS. For the dichotomous endpoints, this will be an observed-case analysis approach using the DEP FAS such that if a participant is missing the data needed to determine the endpoint, they will be considered as not having met the endpoint. For the continuous endpoint, this will be an observed-case analysis. As discussed in [Section 3.14.1.1](#), these analyses will not consider the additional blood Phe data from DEP Weekly substudy.

- **A $\geq 20\%$ reduction from baseline in blood Phe level at the third week of a participant's last 3 weeks at the iTD of SYNB1934v1**

Note that if a participant has 2 Week 3 blood Phe visits at their iTD (i.e., the participant escalated in dose then de-escalated back to their iTD) both Week 3 values will be considered such that the participant can reach the $\geq 20\%$ reduction at either of these assessments.

- **Blood Phe level $\leq 600 \mu\text{mol/L}$ at any time of the iTD of SYNB1934v1**
- **Blood Phe level $\leq 600 \mu\text{mol/L}$ at any time in the DEP**

For each of these endpoints, the number and proportion of participants meeting the corresponding criteria will be summarized along with [REDACTED]. For these endpoints using a $\leq 600 \mu\text{mol/L}$ criterion, the analysis will be performed on those participants with a baseline DEP blood Phe value $> 600 \mu\text{mol/L}$.

- ***Dose level at first blood Phe level $\leq 360 \mu\text{mol/L}$***

The distribution of the dose levels (i.e., 3×10^{11} , 6×10^{11} , 1×10^{12}) when a participant first had a blood Phe level $\leq 360 \mu\text{mol/L}$ will be summarized. The percentage will be two presented ways:

- 1) Based on the DEP FAS with a category for participants who did not reach a blood Phe level $\leq 360 \mu\text{mol/L}$
- 2) Based on the sub-set of participants who reached a blood Phe level $\leq 360 \mu\text{mol/L}$.

- ***Dose level at first $\geq 20\%$ reduction in blood Phe level***

The distribution of the dose levels (i.e., 3×10^{11} , 6×10^{11} , 1×10^{12}) when a participant first had a blood Phe reduction of level $\geq 20\%$ will be summarized. The percentage will be presented ways:

- 1) Based on the DEP FAS with a category for participants who did not reach a blood Phe level $\geq 20\%$
- 2) Based on the sub-set of participants who reached a blood Phe level $\geq 20\%$.

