3.14.2.8 Exploratory Endpoints Analysis

The following are the analysis methods for the set of Exploratory endpoints.

For the dichotomous endpoints, this will be an observed-case analysis approach such that if a participant is missing the data needed to determine the endpoint, they will be considered as not having met the endpoint. For the continuous endpoint, this will be an observed-case analysis.

The following analyses will be performed on the responder RWP FAS

- ***Change from baseline to Week 1 in blood Phe level***

The analysis of the change from RWP baseline to Week 1 in blood Phe level will be a part of the RWP primary efficacy analysis, described in [Section 3.14.2.1](#) for responder RWP FAS.

- ***Percent change from baseline to Week 1, and Week 4 in blood Phe level***

The percent change from RWP baseline to Week 1, Week 3, and Week 4 in blood Phe level, will be analyzed using an MMRM analysis similar to the model described for the RWP primary efficacy analysis ([Section 3.14.2.1](#)), with the dependent variable being the percent change in blood Phe level from RWP baseline, and the RWP baseline blood Phe level as the baseline blood Phe level covariate.

- ***Blood Phe level $\leq 600 \mu\text{mol/L}$ at Week 4***

The proportion of participants meeting the Blood Phe level $\leq 600 \mu\text{mol/L}$ at Week 4 criteria, will be tested between the placebo and SYNB1934v1 treatment groups using a Fisher's Exact test.

The following analyses will be performed on the nonresponder RWP FAS.

- ***Change from baseline to Week 1 and Week 4 in blood Phe level***

The analysis of the change from RWP baseline to Weeks 1 and 4 in blood Phe level will be analyzed as described in [Section 3.14.2.1](#) using the nonresponder RWP FAS.

- ***Percent change from baseline to Week 1 and Week 4 in blood Phe level***

The percent change in blood Phe level from RWP baseline to Week 1 and from RWP baseline to Week 4, will be analyzed using an MMRM analysis similar to the model described for the RWP primary efficacy analysis ([Section 3.14.2.1](#)), with the dependent variable being the percent change in blood Phe level from RWP baseline, and the RWP baseline blood Phe level as the baseline blood Phe level covariate.

- ***Blood Phe level $\leq 360 \mu\text{mol/L}$ at Week 4***

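### The RWP ≤600 endpoint, and to a small extent the DEP ≤360 endpoints, can score as successes people already at or below the threshold at DEP baseline

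*SAP*

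**What the plan says.** **Entry.** Protocol 4.2.1 asks for Phe above 360 µmol/L "on current therapy any time during screening and uncontrolled blood Phe level" above 360 as the mean of the three most recent values. Either laboratory may supply them: "All screening values must be obtained more than 7 days apart, as determined by central or local laboratory". Screening lasts up to 45 days (Protocol 3.6). No threshold applies at DEP baseline.

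**Laboratory used for analysis.** SAP 3.3: "blood Phe levels from the local labs will not be used for analyses but can be used as for the inclusion criterion". Protocol 5.3 stratifies on the central screening value "except for participants where the local screening value was" above 360 and the central one was not; then the local value is used.

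**Analysis sets.** In SAP 3.5 the DEP FAS is everyone enrolled and dosed. The responder RWP FAS adds randomisation, an RWP dose and a fall of at least 20% from DEP baseline. Neither sets a condition on the level of DEP baseline Phe.

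**Endpoints.**
- DEP ≤360 at the iTD, and at any time in the DEP (SAP 3.14.1.7): "For each of these 2 endpoints, the proportion of participants meeting the endpoint will be summarized along with" confidence intervals, on the DEP FAS.
- DEP ≤600 (SAP 3.14.1.8): "the analysis will be performed on those participants with a baseline DEP blood Phe value" above 600.
- Dose level at first ≤360 (SAP 3.14.1.8): no baseline condition.
- RWP ≤600 at Week 4 (SAP 3.14.2.8): Fisher's exact test under the lead-in "The following analyses will be performed on the responder RWP FAS", with no baseline condition.
- RWP ≤360 at Week 4, a key secondary endpoint (SAP 3.14.2.4): Fisher's exact test on the responder RWP FAS, with no baseline condition.

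**The concern.** An endpoint meant to show that people reach a Phe target is hard to read if some were at the target before any drug. The SAP applies a safeguard to the DEP ≤600 endpoints but not to the same threshold in the RWP, nor to the ≤360 endpoints in the DEP.

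The cause differs by threshold. At 600 the overlap follows from the entry rule: anyone habitually at 361–600 is eligible and can be a success on placebo. At 360 it arises only when a later central DEP baseline falls at or below a level that the screening and history values exceeded.

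The stakes differ by study part. The DEP has no control arm, so people already at goal add to the proportion reported as achieving it, and the dose-level table credits them to a dose. In the RWP such people fall in both randomised arms, so the absolute rates change and the difference is usually diluted.

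**Working it through.** The plan gives no expected rate, sample size or power for any ≤360 or ≤600 endpoint, so there is no figure to reproduce. The textual gap needs no arithmetic; its size does.

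**Inputs from the documents.** Entry threshold 360 on one screening value and on a three-value mean; responder = fall of at least 20% from DEP baseline; mean DEP change −11% (Protocol synopsis, sample size).

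**Assumptions, not in the documents.** Habitual off-drug Phe is log-normal with median 550, 700 or 900 µmol/L and between-person log SD 0.45. Visit noise is independent log-normal with CV 10%, 15% or 25%, so log SD = √ln(1+CV²). There is no local/central laboratory bias. For the RWP the reduction e has mean 30% and SD 12 points. Each scenario uses 2,000,000 draws.

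**RWP ≤600.** Keep people with screening >360 and three-value mean >360. Draw DEP baseline B, a Week 3 value and a Week 4 value. Responder: Week 3 × (1−e) ≤ 0.8 × B. Success on active: Week 4 × (1−e) ≤ 600. Success on placebo: Week 4 ≤ 600. Then repeat with B > 600. Entries are percentages; differences are taken before rounding.

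| Median / CV | Responders with B ≤600 | Unrestricted: active, placebo, difference | B >600: active, placebo, difference |
|---|---|---|---|
| 550 / 10% | 45.1 | 81.8, 47.2, 34.7 | 67.0, 12.6, 54.4 |
| 550 / 15% | 41.9 | 80.5, 46.2, 34.3 | 66.8, 18.7, 48.1 |
| 550 / 25% | 36.2 | 77.0, 44.7, 32.2 | 65.5, 27.0, 38.5 |
| 700 / 10% | 29.3 | 68.5, 31.2, 37.4 | 55.5, 8.3, 47.3 |
| 700 / 15% | 27.3 | 67.3, 30.9, 36.4 | 55.2, 12.4, 42.9 |
| 700 / 25% | 23.8 | 64.6, 31.2, 33.3 | 54.7, 18.9, 35.8 |
| 900 / 10% | 15.5 | 50.4, 16.8, 33.6 | 41.3, 4.7, 36.6 |
| 900 / 15% | 14.6 | 49.9, 17.1, 32.7 | 41.4, 7.1, 34.3 |
| 900 / 25% | 12.9 | 48.6, 18.4, 30.2 | 41.7, 11.5, 30.2 |

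The difference grows in eight scenarios and is unchanged in one.

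To see whether the smaller n cancels this, take z = (pA − pP) / √{[pA(1−pA) + pP(1−pP)]/n}, with an assumed 20 responders per arm (the planned number is redacted). At 700 / 15%:
- Unrestricted: 0.364 / √[(0.220 + 0.214)/20] = 2.47.
- Restricted: n = 20 × (1 − 0.273) = 14.5, so 0.429 / √[(0.247 + 0.109)/14.5] = 2.74.

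Across the nine scenarios z rises in seven and falls by at most 0.1 in two.

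**DEP ≤360.** With the same entry rule, 0.5% to 7.8% of participants have DEP baseline ≤360.
- With no drug effect and three Week 3 visits, the proportion ever ≤360 falls by 0.3 to 3.6 points when baseline is restricted to >360. At 550 / 25% it goes from about 17% to about 13%.
- With an 11% reduction at one visit, 1.8% to 13.4% of everyone reach ≤360, against 1.5% to 10.6% of those with baseline >360. Of those reaching it, 19% to 27% were already ≤360 at baseline.

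**RWP ≤360.** With a uniform 30% effect, only 0.3% to 3.5% of responders have DEP baseline ≤360. Success is 9–31% on active and 0.5–8% on placebo unrestricted, against 9–29% and 0.4–7% restricted. There is little here to correct.

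**The case against.** **The entry rule makes 360 and 600 different cases.** People must exceed 360 twice to enter, so a baseline rule is needed at 600 and nearly redundant at 360. This stands, and it is why RWP ≤600 leads this point. It does not explain why the rule used for ≤600 in the DEP is absent for ≤600 in the RWP.

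**A low baseline is not itself a success.** A reader might infer that anyone at goal at baseline is automatically counted. SAP 3.3 scores only post-baseline values. In the simulation, with no drug effect, a person with baseline ≤360 is ≤360 at a given later visit 23–34% of the time, and at any of three visits 48–62%. Such people can count; many will not.

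**Restriction leaves most chance crossings in.** A reader might take the 19–27% share to mean that the DEP result is heavily inflated, or that the fix would clean it. It is a share of a small group. Most who cross by chance have baseline >360 and stay in, because visit-to-visit variation with an any-time rule is the larger driver.

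**Protocol 5.3 is only a stratification rule.** It concerns screening values; entry on a local value comes from Protocol 4.2.1. It shows that discordant laboratories were foreseen, but not that DEP baselines will be ≤360, and no frequency is given. Discordance could raise the ≤360 figures and is not modelled.

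**The endpoints rank low.** DEP ≤360 is listed among the other secondary endpoints, is descriptive and lies outside the testing sequence. RWP ≤600 is exploratory. SAP 2.1 takes its primary evidence from the randomised comparison, and SAP 3.8 tabulates DEP baseline Phe. All of this limits the stakes.

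**Conclusion.** The gap is real on the text: no analysis set conditions on DEP baseline Phe, and the SAP's own safeguard is applied only to the DEP ≤600 endpoints.

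It matters most for RWP ≤600 at Week 4. Under the assumed distributions, restriction cuts placebo success from 17–47% to 5–27%, and the treatment difference moves from 30–37 to 30–54 points. A reader might infer a biased comparison or an inflated type I error. Neither follows, because DEP baseline precedes randomisation and such people fall in both arms.

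For DEP ≤360 and the dose level at first ≤360, the proportion achieving the target is modestly inflated, by about 0.3 to 3.6 points with no drug effect at any of three visits. The key secondary RWP ≤360 test does not need to change.

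Confidence is high in the textual gap. Its size rests entirely on the assumed median, between-person spread and visit noise, and for the RWP on the assumed 30% reduction.

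**What to change.** 1. In SAP 3.14.2.8, restrict the responder analysis of ≤600 at Week 4 to participants with DEP baseline Phe >600, as SAP 3.14.1.8 already does for the DEP. The cost is not trivial: about 13–45% of responders would leave this exploratory analysis under the assumed distributions, although test strength hardly suffers.
2. In SAP 3.14.1.7, and for the dose level at first ≤360 in SAP 3.14.1.8, report the subset with central-laboratory DEP baseline >360, either as the analysis set or beside the DEP FAS result. Few participants leave, and the reported proportion becomes slightly less favourable.
3. Keep the key secondary RWP ≤360 test as planned and add the DEP-baseline >360 subset as supportive only. The planned exact logistic sensitivity analysis does not replace it, because it adjusts for RWP baseline, which is an on-drug value.

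Each change is a sentence of SAP text and needs no new data. Make it before lock and unblinding, so that the choice of denominator cannot look data-driven.
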